6.2 Efficacy Assessments

6.2.1 CGM Measures

Blinded CGM will be performed for 14 continuous days during baseline (ie, from Visit 2 to Visit 3.1) and again for 14 days at the end of the treatment period (ie, from Visit 6 to Visit 7; Section 13.1). The baseline CGM measure will be captured before discontinuing the daily (oral or injectable) or weekly GLP-1 RA, DPP-4i, or down-titration of SU by 50%, and before initiation of Soliqua 100/33 treatment. The blinded CGM device (FreeStyle Libre Pro) will be applied to the back of the upper arm of the participant and activated at Visit 2 (ie, the run-in period). Participants will be required to wear the device continuously for 14 days for baseline CGM data collection, with device removal and data download on Day -1 at their next site visit during the baseline period (ie, Visit 3.1), after collection of C-peptide, insulin, and plasma glucose data from the MMTT. Downloaded CGM data will be reviewed by the investigator to determine the participants' study eligibility. (Note: During the run-in period, CGM device reinsertion will be allowed for participants who do not meet the equivalent of at least 8 days of evaluable CGM data [not necessarily consecutive] over a 14-day period as a result of premature sensor failure [eg, days of CGM device wear × % time CGM device active < 8].) Similarly, participants will be required to continuously wear the device for 14 days at the end of the treatment period from Weeks 14 to 16 (ie, Visit 6 to Visit 7) to collect CGM data, with device removal and data download on the fifteenth day after CGM placement (ie, Visit 7), after collection of only plasma glucose data from the MMTT. Downloaded CGM data will be verified by the investigator at the site to determine participants' study completion. During the end of the treatment period, CGM device reinsertion will also be allowed for participants who do not meet the equivalent of at least 8 days of evaluable CGM data (not necessarily consecutive) over a 14-day period as a result of premature sensor failure (eg, days of CGM device wear \times % time CGM device active < 8), if data can be captured during the 14-day end of treatment window. (Note: The minimum requirement for evaluable CGM data is if at least 10 out of 14 days [not necessarily consecutive] have at least \geq 80% of evaluable CGM data per 24-hour period during the run-in period as well as the end of the treatment period [ie, from Weeks 14 to 16]; Battelino et al 2020.) Criteria for CGM device reinsertion are provided in Table 6-1 and Figure 6-1. Any combination of number of days of CGM device worn and % time CGM device is active (Table 6-1) that results in fewer than 8 equivalent days (defined as ineligibility) of evaluable

CGM data will require device reinsertion. Eligibility and analysis criteria for CGM measures are provided in Section 13.9.

No. of Days CGM Device Worn ^a	Time CGM Device Active (%) ^a	Equivalent Days
8	100	8.00
9	89	8.01
10	80	8.00
11	73	8.01
12	67	8.04
13	62	8.01
14	57	7.98

Table 6-1Criteria for CGM Device Reinsertion

Abbreviations: AGP, Ambulatory Glucose Profile; CGM, continuous glucose monitoring. ^a AGP report.

Figure 6–1 Criteria for CGM Device Reinsertion

Abbreviation: CGM, continuous glucose monitoring.

Participants with less than equivalent of 8 days of evaluable CGM data (not necessarily consecutive) of a 14-day period (eg, days of CGM device wear \times % time CGM device active < 8) during the run-in period will be considered as screen failures. For participants

Sanofi	SOLIQUA TM 100/33
Protocol: LPS16990 (Original, Version 1.0)	18 Aug 2021

who discontinue study treatment prematurely, the visit window can be extended by 14 days to collect the CGM data before they permanently discontinue the treatment.

6.2.2 MMTT-Derived β-Cell Function and PPG Measures

Participants will undergo the MMTT (while wearing the CGM device) to assess maximum PPG exposure in the 4-hour period after the breakfast meal (tested at a central laboratory) with biomarkers of β -cell function (plasma glucose, insulin, and C-peptide) measured at Visit 3.1 (ie, site visit during the baseline period). The baseline MMTT will be conducted before discontinuing the daily (oral or injectable) or weekly GLP-1 RA, DPP-4i, or down-titration of SU by 50%. At Visit 3.1, participants on OADs or an oral or injectable GLP-1 RA will be required to take their dose after the blood sample for FPG and HbA1c is collected and 30 minutes before administration of the meal during the MMTT. Participants on weekly GLP-1 RA should have their baseline MMTT conducted within 7 (\pm 3) days after their last dose. During baseline (Visit 3.1), blood samples will be collected at the following time points: premeal (30 min) and just before administration of OADs or GLP-1 RA (oral or injectable) (baseline); time 0 (just before meal administration), 10 min, 20 min; and 0.5, 1.0, 1.5, 2.0, 2.5, 3.0, and 4.0 hours post-meal for plasma glucose, C-peptide, and insulin levels.

At the end of the treatment period (Visit 7), participants will again undergo the MMTT (while wearing the CGM device; only to derive PPG measures). Soliqua 100/33 should be administered 30 minutes before administration of the meal during the MMTT at Visit 7. At the end of the treatment period (Visit 7), blood samples will be collected for plasma glucose levels, as follows: premeal (30 min) and just before administration of Soliqua 100/33; and time 0 (just before meal administration), 0.5, 1.0, 1.5, 2.0, 2.5, 3.0, and 4.0 hours post-meal. These values will be used for PPG analyses with the goal of deriving reduction in the maximum glucose exposure in the 4-hour period after the breakfast meal following Soliqua 100/33 administration at Week 16 compared with baseline. During both baseline and end-of-treatment assessments, removal of the CGM device and download of data will be done after completion of the MMTT (Section 13.1).

The MMTT includes a standardized meal (ie, Boost Very High Calorie) that contains approximately 530 kcal and is composed of 19% carbohydrates, 44% protein, and 33% fat. The composition and the quantity of the standardized meal must be identical throughout the study period.

During the baseline period (ie, Visit 3.1), on the day of the MMTT, the participants must not eat any food or drink, except water, for at least 8 hours before the scheduled meal test (to be completed in the morning). At the end of the treatment period (ie, Visit 7), the MMTT will also be performed in a fasted state (eg, no consumption of any food or drink for at least 8 hours, except water, before the scheduled meal test), and participants will receive their Soliqua 100/33 dose at the study site 30 minutes before the start of the test (ie, consumption of the meal and just after the first blood draw).

For participants who discontinue study treatment prematurely, the visit window can be extended by 14 days to collect the CGM data, followed by the MMTT data, before they permanently discontinue the treatment.

6.2.3 Fasting SMPG

Participants will be supplied with a glucometer kit and an eDiary at the screening visit. Appropriate training will be provided to the participants related to proper use of the glucometer and eDiary completion. Fasting SMPG values (lowest values in conjunction with measurements from the previous 3 days) will be used to titrate and adjust Soliqua 100/33 doses and monitor glycemic control. Sound clinical judgment should be exercised during titration to further up-titrate if the lowest value from the last 3 measurements is between 80 to 100 mg/dL but the 2 other values are above 100 mg/dL and further titration is required to manage hyperglycemia. The participants are required to measure fasting SMPG values before breakfast at least 3 to 4 times per week throughout the study period (to inform each dose adjustment) and record the results in the eDiary. During the titration period, fasting SMPG should be performed on each of the 3 to 4 days before each dose adjustment. (Note: Additional titration is at the discretion of the investigator with the goal of achieving glycemic targets while minimizing the risk of hypoglycemia and hyperglycemia.)

6.2.3.1 SMPG During Symptomatic Hypoglycemia

Whenever participants experience hypoglycemia symptoms, they (or others, if applicable) should measure plasma glucose, if possible. Participants should be instructed to measure plasma glucose levels before carbohydrate intake/administration of glucose whenever symptomatic hypoglycemia is suspected, unless safety considerations necessitate immediate carbohydrate/glucose rescue before confirmation with the SMPG values. Participants must contact the investigator as soon as possible following hypoglycemia events for review and so

Property of the Sanofi Group - strictly confidential

that a decision regarding any necessary actions can be made. Participants should be instructed to measure plasma glucose levels again after the event resolves.

6.2.4 FPG Measurements

Blood samples will be collected to determine FPG at the time points specified in the SoE (Section 13.1) and will be measured at a central laboratory. For the scheduled site visits, participants are required to arrive fasting without administering the Soliqua 100/33 injection. Fasting is defined as no food intake in the 8 hours before blood sampling, except water.

6.2.5 HbA1c Measurements

Blood samples will be collected to measure HbA1c during the screening and run-in periods and at Visit 3.1 (before administration of the meal) at the central laboratory, to determine study eligibility and at the end of the 16-week treatment period (Visit 7), to determine change in glycemic control.

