3.1 Study Design

This is a 16-week, multicenter, interventional, open-label, single-arm, Phase 4 study using blinded CGM (FreeStyle Libre Pro) to demonstrate improvement in the percentage of TIR from baseline in patients adding Soliqua 100/33 and treated for 16 weeks. The study will be conducted in approximately 100 patients whose T2DM is very uncontrolled on 2+ OADs with or without GLP-1 RAs (with stable doses for 3 months), as evident from a screening HbA1c of \geq 9%-13%. The study will attempt to represent the diversity of the US patient population with T2DM **through site recruitment efforts**.

All eligible participants will undergo 14 days of blinded continuous CGM monitoring at baseline (the run-in period) and a mixed-meal tolerance test (MMTT) while on baseline medications. Soliqua 100/33 treatment will be initiated on Day 0 (Visit 3.2), after the MMTT (which is scheduled at Visit 3.1; Figure 3–1). Sulfonylurea (SU) doses should be down-titrated by 50% when starting Soliqua 100/33, and the last doses of daily dipeptidyl peptidase-4 inhibitor (DPP-4i) and daily GLP-1 RA (oral or injectable) should be administered on the morning of Day –1, the day before the first dose of Soliqua 100/33.

At Visit 3.1, participants on OADs or an oral or injectable GLP-1 RA will be required to take their dose after the blood sample for fasting plasma glucose (FPG) and HbA1c is collected and 30 minutes before administration of the meal during the MMTT (during which measures for both β -cell function and postprandial glucose [PPG] analyses will be captured). Participants on a weekly GLP-1 RA should have their baseline MMTT conducted within 7 (± 3) days after their last dose and administer their last weekly GLP-1 RA dose 7 (± 2) days before the first dose of Soliqua 100/33.

The dose of Soliqua 100/33 will be adjusted during the titration period (ie, from Weeks 1 through 12; Visits 4.0 to 5.4), at the investigator's discretion until the desired fasting SMPG value (80-100 mg/dL) is achieved.

During the end of the treatment period (from Visit 6 to Visit 7), participants will again be required to undergo 14 days of blinded continuous CGM monitoring and a MMTT (only to derive PPG measures). Soliqua 100/33 should be administered 30 minutes before

administration of the meal during the MMTT at Visit 7 (during which only measures for PPG analyses will be captured).

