3.1.2 Duration of Study Participation for Each Participant

The study comprises the following periods (further detailed in the graphical study diagram [Figure 3–1] and the schedule of events [SoE; Section 13.1]):

- A screening period of up to 2 weeks.
- A run-in period of 2 weeks, including the baseline period.
 - At Visit 2, the CGM device will be applied to the back of the upper arm of the participant and baseline CGM data will be collected continuously for 14 days; the

device will be removed at the subsequent site visit during the baseline period (ie, Visit 3.1), after the MMTT.

- During the baseline period, on Day -1 (Visit 3.1), participants will return to the site for the MMTT (for both β-cell function and PPG measures) and CGM removal and data download (after the MMTT). Dispensing of the Soliqua 100/33 pen and instruction on administration of Soliqua 100/33 will also take place during this visit.
- Visit 3.2 (ie, Day 0) during the baseline period is the first day of Soliqua 100/33 administration and includes a phone contact to ALL participants to ensure all administration procedures were successfully executed and to answer any questions. (Note: The first day of Soliqua 100/33 administration [ie, Visit 3.2, Day 0] for participants on weekly GLP-1 RA will depend on their administration schedule and may not be the day immediately following Visit 3.1. Soliqua 100/33 administration for these participants should be 7 [± 2] days after their last weekly GLP-1RA dose.)
 - A phone contact should also be made ONLY to participants on weekly GLP-1 RA on the day before Soliqua 100/33 initiation, to remind them of the next morning's injection and to provide instructions for SoloStar pen use. The participants will provide their concomitant medication details to the site personnel over the phone.
- A 16-week open-label treatment period.
 - Visit 3.2 (ie, Day 0) is the first day of Soliqua 100/33 administration and begins the open-label treatment period (with different initiation requirements based on weekly or daily GLP-1 RA use, as explained above).
 - The dose of Soliqua 100/33 will be adjusted during the titration period (ie, from Weeks 1 through 12; Visits 4.0 to 5.4), at the investigator's discretion, until the desired fasting SMPG value (80-100 mg/dL) is achieved (Table 5-1).

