4.1 Inclusion Criteria

Each participant must meet all of the following criteria to be enrolled in this study:

- 1. Is capable of understanding the written informed consent, provides signed written informed consent, is willing and able to complete the electronic diary (eDiary), and agrees to comply with protocol requirements (confirmed by the site staff performing the recruitment efforts).
- 2. Is an adult ≥ 18 years of age.
- 3. Has an HbA1c \geq 9%-13% during the run-in period.
- 4. Was diagnosed with T2DM at least 6 months before the baseline period.
- 5. Has been treated with 2+ OADs with or without GLP-1 RAs with stable doses (for both) for 3 months before the screening period.
- 6. Is willing and able to wear the CGM device continuously for 14 days to capture CGM measures at baseline (from Visit 2 [ie, the run-in period] until the next site visit at Visit 3.1) and again at the end of the treatment period [ie, from Visit 6 until the next site visit at Visit 7; Section 13.1).
- 7. Is willing and able to prick fingers a minimum of 2 to 4 times per week, using sterile lancets provided with a manual blood glucose meter kit.
- 8. Is willing to discontinue daily (oral or injectable) or weekly GLP-1 RA or DPP-4i before administration of Soliqua 100/33.

9. Is willing and able to inject Soliqua 100/33 and increase dose as needed to achieve SMPG target.

10. If female, is not pregnant or breastfeeding and one of the following conditions applies:

- Is a woman of non-childbearing potential (WONCBP), as defined in contraceptive and barrier guidance (Section 13.7).
- Is a woman of childbearing potential (WOCBP) and agrees to use a contraceptive method that is highly effective, with a failure rate of <1%, as described in contraceptive and barrier guidance (Section 13.7), during the study treatment period (to be effective before starting the study drug) and for at least 1 week after the last administration of study drug.
 - A WOCBP must have a negative urine pregnancy test at both screening and baseline visits. (Note: If a urine test cannot be confirmed as negative [eg, an ambiguous result], a serum pregnancy test is required. In such cases, the participant must be excluded from participation if the serum pregnancy result is positive.)

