5.5 Treatments Administered

- Time of administration:
 - Soliqua 100/33 should be self-administered once-daily in the morning approximately 60 minutes before breakfast.
 - The first dose of Soliqua 100/33 will be administered on the morning of Day 0 (ie, Visit 3.2). This date should be 7 [± 2] days after the last weekly GLP-1 RA dose or the morning following the last dose of DPP-4i or daily GLP-1 RA (oral or injectable) administration.

Starting dose

• For all participants, the starting dose of Soliqua 100/33 will be 15 units of insulin glargine (corresponding to 5 µg of lixisenatide).

• The maximum daily dose of Soliqua 100/33 should not exceed 60 units of insulin glargine (corresponding to 20 µg of lixisenatide).

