6.5 Sample Collections

Site personnel will collect blood samples at the visits specified in the SoE (Section 13.1). These samples will be processed at the site and shipped the same day to a central laboratory, as specified in the laboratory manual. The central laboratory will analyze blood samples for PPG measures, HbA1c, and FPG, clinical chemistry, hematology, and biomarkers of β -cell function (during the MMTT). Results will be returned to the site within 48-72 hours.

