8.4 Analysis Sets

The following analysis sets will be used in the statistical analyses:

- Enrolled set: All eligible participants who are dispensed Soliqua 100/33 and sign the ICF.
- Efficacy analysis set: All enrolled participants who receive ≥1 dose of Soliqua 100/33 and have evaluable CGM data at baseline.
- Safety set: All enrolled participants who receive ≥ 1 dose of Soliqua 100/33.

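### The Day -1 HbA1c is labelled an eligibility test, but its result is due after dispensing and usually after the first dose, and the safety set is limited to eligible participants

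*Protocol*

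**What the plan says.** **Eligibility.** Protocol 6.2.5 and footnote n of the Schedule of Events (13.1) list HbA1c at screening, in the run-in and "at Visit 3.1 (before administration of the meal) at the central laboratory, to determine study eligibility". The Schedule also ticks the inclusion and exclusion criteria at Visit 3.1. Inclusion criterion 3 (4.1) asks for an HbA1c of "9%-13% during the run-in period". Section 3.1 describes the population "as evident from a screening HbA1c of" 9-13%. Section 3.1.2 places Visit 3.1 inside the run-in.

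**Timing.** Visit 3.1 is Day -1. On the pen, 3.1.2 says: "Dispensing of the Soliqua 100/33 pen and instruction on administration of Soliqua 100/33 will also take place during this visit". Section 5.5 puts the first dose on the morning of Day 0. For weekly GLP-1 RA users, Day 0 "may not be the day immediately following Visit 3.1". Section 6.5 names HbA1c among the central laboratory tests and says: "Results will be returned to the site within 48-72 hours".

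**Analysis sets.** Protocol 8.4 defines the enrolled set as "All eligible participants who are dispensed Soliqua 100/33 and sign the ICF"; the efficacy and safety sets are subsets of it. SAP Table 4 keeps these three and adds a Screened set of everyone who signed consent.

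**The concern.** A site that follows the calendar doses most participants before it holds a result that the protocol calls an eligibility result. No section tells the site to wait, says which HbA1c governs if the three disagree, or says how to analyse a dosed participant whose Visit 3.1 value is out of range. Waivers are not permitted (Section 4), and 11.2.2 treats a breach of entry criteria as a significant deviation leading to withdrawal, so a late out-of-range value has consequences.

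The main stake is the safety denominator. If *eligible* is applied after the fact, a treated participant drops out of the treatment-emergent adverse event and hypoglycemia tables because of a result learned after treatment began. Those affected would almost all be people whose HbA1c had moved below 9% before treatment. A second stake is the HbA1c change endpoint: the Visit 3.1 value is also the HbA1c baseline (last value before first injection, Protocol 8.7 and SAP 4.1), so selecting on it raises the baseline mean. A third is that sites could apply different entry rules.

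**Working it through.** **1. The plan's own figure.** For the one-sample test on TIR change, n = (SD × (z0.975 + z0.95) / difference)² = (25 × (1.960 + 1.645) / 10)² = 81.2, so 82, as stated. With 15% loss, 82 / 0.85 = 96.5, so 97 against the stated 100. The sample size is sound and is not the issue.

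**2. Timing (6.5, 3.1.2, 5.5).** Take the blood draw at Visit 3.1 as hour 0.
- Pen dispensed: same visit.
- First dose, next-morning starters: about hour 24.
- Result: hour 48 to 72, if the clock starts at the draw; later if it starts at receipt.
- Gap after first dose: 48 - 24 = 24 hours to 72 - 24 = 48 hours, with 1 to 3 daily doses due by then.
- Weekly GLP-1 RA users: the baseline MMTT falls 7 ± 3 (4 to 10) days and the first dose 7 ± 2 (5 to 9) days after the last weekly dose. The first dose can be up to 9 - 4 = 5 days after Visit 3.1, so for some of them the result arrives first.
- Visit 2 value: drawn on Day -15, back by about Day -12, well before dispensing.

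**3. Where a dosed, out-of-range participant is counted.**

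| Text | Consequence |
|---|---|
| Protocol 8.4, SAP Table 4 | Not *eligible*, so not enrolled, and outside the efficacy and safety sets |
| SAP 4.2, screen failures | Tied to drug not being dispensed, so this participant is not a screen failure |
| SAP 5.4.5 | Enrolment occurs at Visit 3.2, the first-dose visit, so enrolled |
| SAP 5.3.1 with Protocol 11.2.2 | Significant deviations, which can include entry breaches, are summarised in the enrolled set, so enrolled with a deviation |
| SAP 4.2, disposition | Plans a count of exposed but non-enrolled participants, so the category is foreseen |
| SAP 4.7.2, listings | Plans an adverse event listing for treated, non-enrolled participants, but bases it on the safety set, which cannot contain them |

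**4. How many.** Simulation: true HbA1c normal with mean 9.0, 9.5 or 10.0% and SD 1.2; independent visit-to-visit error with SD 0.1 to 0.4. All of these are assumptions. Among those inside 9-13% at both screening and Visit 2, the share outside at Visit 3.1 runs from about 1% (mean 10.0, error SD 0.1) to 8.5% (mean 9.0, error SD 0.4), or roughly 1 to 8 per 100 dosed.

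**5. Effect on the HbA1c baseline.** Mean of observed minus true value at Visit 3.1 among those selected:
- all three values select: 0.001 to 0.042 points;
- Visit 3.1 alone selects: 0.003 to 0.100;
- only screening and Visit 2 select: 0.

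Against the 0.8-point fall used in planning, 0.042 / 0.8 = about 5%.

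**6. Effect on power.** Remove a share of 100 dosed participants, then lose 15% of the rest; noncentral t with 10 / 25 = 0.4.

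| Removed | Left | Power |
|---|---|---|
| 0% | 85 | 95.4% |
| 5% | 80 | 94.2% |
| 10% | 76 | 93.1% |

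**The case against.** The best reply is that the working criterion is already met before dosing. Inclusion 3 asks for a value in the run-in, not at every visit; Protocol 6.1 places the run-in HbA1c at Visit 2; and 6.2.5 lists the run-in and Visit 3.1 separately. On that reading the Visit 2 result qualifies, and the fault is loose wording about the purpose of the Visit 3.1 sample. This is a fair reading and it supports the remedy. It does not settle the matter, because 6.2.5 and footnote n still give the Visit 3.1 sample an eligibility purpose, the Schedule puts Visit 3.1 under run-in, and the criteria are rechecked there.

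The second reply is that removal from the analysis sets depends on a literal reading of one word, and SAP 4.2, 5.3.1 and 5.4.5 favour keeping the participant as enrolled with a deviation. That stands: exclusion is one reading, not a certainty. What remains is that the set definitions say otherwise, so the tabulated safety population depends on which section is followed.

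Three stronger inferences are tempting and not supported.
- That such a participant leaves every analysis set: the SAP Screened set still holds them, although SAP 4.7.2 uses it only for pre-treatment safety data.
- That everyone is dosed before the result: some weekly GLP-1 RA users start later.
- That HbA1c change is inflated by up to 0.10 points: that needs Visit 3.1 to be the only selecting value, whereas 6.2.5 names all three.

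**Conclusion.** The timing conflict holds on the documents' own dates: the rule as worded cannot operate on the schedule as written, except for weekly GLP-1 RA users who start late enough for the result to precede the first dose. Even for them the pen has already been dispensed. The qualifying HbA1c is also inconsistent across 3.1, 4.1 and 6.2.5.

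The consequence for the analysis sets is an unresolved contradiction. Its practical weight is in safety reporting, where the one planned output for this group is tied to a set that excludes them. The number affected, about 1 to 8 per 100, rests wholly on the assumed HbA1c mean, spread and visit error. The effect on HbA1c change is at most about 0.04 points if all three values select, on an endpoint that the SAP classes as tertiary/exploratory and leaves outside the testing hierarchy. A reader might infer that the primary result is compromised. It is not: the TIR baseline comes from run-in CGM rather than this HbA1c, and power stays at 94.2% even if 5% were removed. The point should be corrected, but it does not threaten the trial's main conclusion.

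**What to change.** 1. **Safety set.** In Protocol 8.4 and SAP Table 4, define it as all participants who received at least one dose, without *enrolled* or *eligible*. Base the SAP 4.7.2 adverse event listings on that set, and state that a dosed participant later found to breach an entry criterion stays in it and is reported as a deviation.
2. **Eligibility.** Reconcile 3.1, 4.1(3), 6.2.5 and footnote n so that eligibility rests on one named HbA1c whose result is available before dispensing. The Visit 2 run-in value is already collected and fits inclusion 3. Label the Visit 3.1 HbA1c as the efficacy baseline only.

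The cost is amendment and SAP wording. No sample or visit is added, and no dose, dosing date or HbA1c threshold changes. The downside is that a few participants slightly outside 9-13% at Visit 3.1 stay in the analysis. In return, under the independent-error assumption above, a baseline value that plays no part in selection carries no selection shift.
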